Secondary Endpoints	
 
1. Incidence of progressive disease within or at the planned tumor volume (PTV) margin (i.e. local control)
 
2. Incidence of progressive disease within any section of the liver, including the PTV (e.g. intrahepatic disease free survival)
 
3. Incidence of progressive disease outside of the liver (e.g. extrahepatic disease free survival)
 
4. Overall Survival
 
5. Proportion of participants that proceed to transplantation
 
6. Incidence of non-classical radiation-induced liver disease (RILD), defined as grade 4 aspartate aminotransferase or alanine aminotransferase elevation, or an increase in CP score of <math>\geq 2</math> within 1 week to 3 months after completing SBRT.
 

	7. Incidence of liver toxicity per CTCAE v5.0 within 1 week to 3 months after completing SBRT.
Exploratory Endpoints	
 
1. QoL scores for EORTC QLQ-C30 questionnaire
 
2. QoL scores for Functional Assessment of Cancer Therapy-Hepatobiliary (FACT-Hep) questionnaire
 
3. At time of transplantation, histopathologic changes in irradiated tumor sites relative to uninvolved liver tissue will be assessed
 

Number of Participants	15
Duration of Therapy	SBRT will be administered as 5 fractions every other day (~10 day)
Duration of Follow Up	Time of progression, or transplantation, or 2-years after last SBRT dose, whichever occurs first
Key Inclusion Criteria	
 
1. Participants aged <math>\geq 18</math> years
 
2. Patient diagnosed with HCC and recommended for LTX
 
3. Meets clinical criteria for eligibility for SBRT to the target lesion
 
4. Childs-Pugh Class B8 or higher
 
5. Eastern Clinical Oncology Group performance status <math>\leq 2</math>
 
6. Safe radiation treatment planning parameters that adhere to all organs at risk constraints per section 5.1 of the protocol. If normal organs at risk constraints (including at least 700cc of uninvolved liver) are unable to be met at the lowest dose modification (30 Gy in 5 fractions), the patient is deemed ineligible for SBRT and deemed a screen failure.
 

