##### 3.2.2 SECONDARY ENDPOINTS

Endpoint	Start	End
1. Localized control rate: Incidence of progressive disease within or at the planned tumor volume (PTV) margin		Time of progression, transplantation, death or 2-years after last SBRT dose, whichever occurs first.
2. Incidence of intrahepatic progressive disease		
3. Incidence of extrahepatic progressive disease		
4. Proportion of participants that proceed to transplantation	First dose of SBRT	
5. Overall Survival		Time of death or 2-years after last SBRT dose
6. Incidence of non-classic RILD, defined as grade 4 aspartate aminotransferase or alanine aminotransferase elevation, or an increase in CP score of $\geq 2$ within 1 week to 3 months after completing SBRT (Appendix A)		3 months after last SBRT dose

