## 4. STUDY ENROLLMENT AND WITHDRAWAL

### 4.1 PARTICIPANT INCLUSION CRITERIA

To be eligible to participate in this study, an individual must meet all of the following criteria:

1. Ability to understand and the willingness to sign a written informed consent document.
2. Age  $\geq 18$  years at time of informed consent. All people regardless of biologic sex and members of all races and ethnic groups will be included.
3. Must be listed or recommended to be listed for orthotopic liver transplantation at the participating institution
4. Have a CP score  $\geq B8$ , as defined in Appendix A
5. Eastern Clinical Oncology Group (ECOG) performance status  $\leq 2$ , or Karnofsky Performance Scale  $>60$  (refer to Appendix B)
6. Must have a life expectancy  $> 12$  weeks
7. Safe radiation treatment planning parameters that adhere to all organs at risk constraints per section 5.1 of the protocol. If normal organs at risk constraints (including at least 700cc of uninvolved liver) are unable to be met at the lowest dose modification (30 Gy in 5 fractions), the patient is deemed ineligible for SBRT and deemed a screen failure.
8. Except for prior radiotherapy or radioembolization, other prior therapies to previously treated lesions, are permitted.
9. People of childbearing potential must have a negative urine or serum pregnancy test within 72 hours prior to receiving the first dose of SBRT. If the urine test is positive or cannot be confirmed as negative, a serum pregnancy test will be required.

Participants of childbearing potential are those who have not been surgically sterilized or have not been free from menses for  $>1$  year without an alternative medical cause.

*Note: Abstinence is acceptable if this is the preferred contraception for the participant.*

10. No other prior invasive malignancy is allowed except for the following: adequately treated basal (or squamous cell) skin cancer, in situ breast or cervical cancer. Stage I or II invasive cancer treated with a curative intent without evidence of disease recurrence for at least five years.

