## 6.8 SCHEDULE OF EVENTS

Visit Days	Screening	Treatment					Follow-Up B (±4 weeks)	
	Days -28 to -1	Days † (+7 days)						
		1	3	5	7	9*		
SBRT A		X	X	X	X	X		
Informed consent	X							
Inclusion/exclusion criteria	X							
Medical history	X						X B	
Prior/concomitant medications	X						X B	
Physical Examination C	X						X B	
Radiographic Imaging	X	X D	X D	X D	X D	X D	X E	
Hematology F	X						X B	
Biochemistry G	X						X B	
Coagulation	X						X	
Pregnancy test	X							
Fiducial placement (if needed)	X							
AE assessment	X	X					X	
EORTC QLQ-30	X						X B	
FACT-Hep	X						X B	

† Starting on day 1, SBRT dose fractions are given every other day (i.e., Monday-Friday), but not administered on Saturdays, Sundays, or holidays. Dosing interruptions because of weekends and holidays will be recorded in CRF.

\*Day 9 study assessments of radiographic imaging and AE collection will serve as Early Termination and/or End of Treatment Visit.

A Scheduled SBRT visits may be delayed by no more than 7 days between each visit, or may occur earlier than scheduled by no more than 3 days.

B Follow-up assessment to occur 6 weeks following completion of SBRT then every 3 months up to 2 years post SBRT therapy

C All physical exams will include assessing weight, vital signs, and ECOG performance status. Height will be measured at screening visit only.

DCone-beam CT will be obtained prior to each SBRT fraction.

E Participants will undergo surveillance imaging (e.g., CT scan) 6 weeks following completion of SBRT and then every 3 months for the first 2 years.

F Hemoglobin, platelets and white cell count with differential white count

G Biochemistry to include renal (creatinine, urea, sodium, potassium) and liver function (AST, ALT, bilirubin)

HAEs and laboratory safety measurements will be graded per NCI CTCAE version 5.0 as well as definition of radiation-induced liver disease (Child-Pugh elevation of 2 or more). All AEs, whether gradable by CTCAE or not, will also be evaluated for seriousness. Record all AEs and SAEs occurring from the time of consent signing to 3 months following the completion of SBRT.

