## **8.4 ADVERSE EVENT LIST(S)**

### **8.4.1 ADVERSE EVENT LIST FOR SBRT**

Rates of non-classical RILD (defined as a CP elevation of 2 or more within 3 months after radiation) are reported to be in the range of 20-30%.

Rates of Grade CTCAE 1-2 toxicities are reported to range from 0-27% and Grade 3-4 toxicities are observed in around 5%. The most commonly reported toxicities are fatigue, right upper quadrant pain, low-grade pyrexia, and elevation in transaminase. Minor pain, fever and chills (Grade 1) is observed in 14% of patients. Gastric ulceration and esophagitis occurred at rates of 7% (Grade 2) and 3% (Grade 3), respectively.

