#### 9.2.3 ANALYSIS OF THE SECONDARY ENDPOINTS

Using the efficacy analysis set, the estimate of local control rate, intrahepatic progression free survival, and overall survival, will be plotted using Kaplan-Meier curve and reported with median survival and 95% CI if available. Using the same efficacy analysis set, the proportion of participants that proceed to transplantation, will be measured and reported with 95% CI.

Non-classic RILD, liver toxicity defined as a  $\geq 2$  increase in CP score (**Appendix A**), and liver toxicity per CTCAE v5.0, will be estimated along with an exact CI using the safety analysis set.

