## APPENDIX A: CHILD-TURCOTTE PUGH SCORE

The Child-Turcotte-Pugh (CP) scoring system utilizes the serum bilirubin, serum albumin, prothrombin time (PT)/ international normalized ratio (INR), degree of ascites and degree of hepatic encephalopathy and assigns 1–3 points for each variable. Patients are divided into three classes based on total points with  $\leq 6$ , 7–9, and  $\geq 10$  points representing Child's class A, B, and C, respectively.

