### Child-Pugh-Turcotte Score

	Variable score 1	Variable score 2	Variable score 3
Serum albumin (g/dL)	>3.5	2.8–3.5	<2.8
Ascites	Absent	Mild to moderate (diuretic controlled)	Severe (diuretic refractory)
Prothrombin time (INR)	<1.7	1.7–2.3	>2.3
Encephalopathy	Absent	Mild to moderate (grade 1–2)	Severe (grade 3–4)
Total bilirubin (mg/dL)	<2	2–3	>3

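### The Child-Pugh-rise part of the RILD endpoint loses sensitivity from B8 upward and cannot be met at scores 14-15; component changes should be reported beside it

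*Combined protocol and SAP*

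**What the plan says.** - **Endpoint.** Section 3.2.2 has non-classic RILD "defined as grade 4 aspartate aminotransferase or alanine aminotransferase elevation, or an increase in CP score of" 2 or more, from 1 week to 3 months after SBRT. There are thus two routes to an event. The Schedule of Events (6.8) gives only the second, in its "definition of radiation-induced liver disease (Child-Pugh elevation of 2 or more"), and so does 8.4.1.
- **Scale.** Appendix A "assigns 1–3 points for each variable" and has five variables, so totals run from 5 to 15. The 3-point categories for albumin, INR and bilirubin are open-ended (below 2.8 g/dL, above 2.3, above 3 mg/dL), and the top ascites category is simply "Severe (diuretic refractory").
- **Population.** The Synopsis asks for "Childs-Pugh Class B8 or higher", and inclusion criterion 4 in 4.1 agrees. Neither sets a maximum score.
- **Analysis.** Section 9.2.3 reports RILD, the Child-Pugh rise and CTCAE liver toxicity as proportions; each "will be estimated along with an exact CI using the safety analysis set". Under 9.1 that set is everyone from the first fraction. Baseline score and room to rise are not mentioned.

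**The concern.** A rise of 2 points can be recorded only by items that still have room. Someone who enters with bilirubin at 4 mg/dL already has 3 points for it; if bilirubin reaches 20 mg/dL the item still scores 3. The transaminase route does not see that change either, nor a fall in albumin or a lengthening INR. At a total of 14 or 15 the Child-Pugh route is closed altogether, but the participant is still counted as evaluable and event-free on it.

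The trial enrols the part of the scale where this happens most, and its secondary objective includes toxicity in advanced cirrhosis. A reader of the final report could not tell a participant whose liver function held steady from one whose score had no room to show a decline.

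**Working it through.** **The plan's own figure.** The plan gives no design figure for RILD. Its one design figure is n = 15 (9.3.1), chosen to meet at least one plan that fails the constraints when the failure probability is 0.20. That reproduces: 1 - 0.80^15 = 0.965, and ln(0.05)/ln(0.80) = 13.4, so 14 would suffice. It does not depend on the RILD endpoint.

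**Inputs from the documents.** Five items scored 1 to 3 (Appendix A); baseline 8 or more with no ceiling (4.1); event threshold of 2 points (3.2.2).

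**Assumptions, not in the documents.** All 3^5 = 243 item profiles are listed, and profiles with the same total get equal weight. Each item below 3 worsens by one category, independently, with probability q. For a profile with m items below 3,

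P(rise of 2 or more) = 1 - (1 - q)^m - m q (1 - q)^(m-1).

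**Worked case, score 8, q = 0.2.** Of 30 profiles, 10 have no item at 3 (m = 5) and 20 have one (m = 4), so 20/30 = 67% have an item at its cap.

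- m = 5: 1 - 0.328 - 0.410 = 0.263
- m = 4: 1 - 0.410 - 0.410 = 0.181
- Average: (10 × 0.263 + 20 × 0.181)/30 = 0.208

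**All scores.** The fourth and fifth columns fix q so that score 8 gives 20% (the low end of 8.4.1; q = 0.195) or 31% (the site figure in 1.4.1; q = 0.257). The last column is the q needed to hold 31% at that score.

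| Baseline score | Headroom (15 - score) | Profiles with an item at 3 | P, q = 0.195 | P, q = 0.257 | q to hold 31% |
|---|---|---|---|---|---|
| 8 | 7 | 67% | 20% | 31% | 0.26 |
| 9 | 6 | 89% | 17% | 26% | 0.29 |
| 10 | 5 | 98% | 13% | 21% | 0.33 |
| 11 | 4 | 100% | 9% | 16% | 0.39 |
| 12 | 3 | 100% | 6% | 10% | 0.48 |
| 13 | 2 | 100% | 3% | 4% | 0.68 |
| 14 | 1 | 100% | 0% | 0% | none |
| 15 | 0 | 100% | 0% | 0% | none |

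Two results need no model: every profile at 11 or above has an item at its cap, and the last two rows are zero for any q. The decline from 8 to 13 does need the model. It is also only an average: at q = 0.2 a C10 profile of 2-2-2-2-2 (m = 5) gives 26%, while a B8 profile of 1-1-1-2-3 (m = 4) gives 18%.

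**Illustrative size at n = 15, q = 0.257.** Without a cap the rate would be 38% (m = 5 for everyone). Three invented baseline mixes give:

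- 7, 5, 2 and 1 participants at scores 8 to 11: 27%
- 3, 4, 4, 2 and 2 at scores 8 to 12: 22%
- 2, 4, 4, 3 and 2 at scores 9 to 13: 16%

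That is about 1.7 to 3.4 fewer events among 15. For comparison, the exact 95% CI for 4/15 is 8% to 55%. These are Child-Pugh-rise rates only; the AST/ALT route is not modelled.

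**The case against.** The case against making much of this is good on several counts.

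- **Room remains for most scores.** A B8 participant has 7 points of headroom, and a rise of 2 is possible up to 13. A reader might infer that the score is exhausted throughout the enrolled population; it is not.
- **The highest scores should be rare.** Score 15 needs grade 3-4 encephalopathy. With encephalopathy at 2 points or fewer, only one of the 243 profiles reaches 14. Such a person must also have ECOG 2 or better (or the Karnofsky alternative) and a life expectancy above 12 weeks, and inclusion criterion 1 asks for capacity to consent, although 4.5 allows a representative.
- **A falling rate is not shown.** A reader might infer that RILD must fall as baseline worsens. That requires the same per-item risk at every score. The series cited in 1.4.1 has 26% at Child-Pugh A and 7 of 13 at B7, and the site cohort in 1.2.1 found no significant difference between B8 or higher and A/B7. These data give no rates within B8 to C15, so they do not show that the cap is harmless, but they do not support an automatic decline.
- **A bias toward safety is not shown.** Section 1.4.1 concedes that natural decline is hard to separate from treatment toxicity. With no control arm that decline counts as RILD and pushes the rate up.
- **CTCAE liver toxicity is in the same sentence of 9.2.3.** The site series in 1.4.1 shows CTCAE grading picking up grade 4 hyperbilirubinemia and encephalopathy. This covers part of the gap. How much is unclear, because the plan does not say which terms or grades count as liver toxicity.
- **No comparison is planned.** RILD rates that "are reported to be in the range of 20-30" percent appear in 8.4.1 as an expected-event list, not as a benchmark for a test.

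What survives is narrower: the cap is real, the plan is silent on it, and a confidence interval, however wide, does not describe worsening that the score cannot register.

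**Conclusion.** The point holds in a limited form. In a B8-or-higher population the Child-Pugh-rise criterion loses sensitivity as more items sit at 3 points, and it is unattainable at 14-15, where participants (probably few) remain in the denominator as non-events. The AST/ALT route does not fill this gap, and the CTCAE proportion fills it in part.

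The structural facts rest on Appendix A, 4.1 and 9.1 alone. The percentages below 14 rest on equal profile weights and a common, independent per-item risk, neither of which the documents supply. Without a baseline score distribution, and with risk that may rise with severity and natural decline acting the other way, neither the size nor the net direction of bias in the RILD estimate can be stated. This is a cheap reporting improvement; the sample size and the primary endpoint are unaffected.

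**What to change.** In 9.2.3, keep all three planned proportions in the full safety set, as 9.1 requires, and add:

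1. A per-participant listing or table of baseline Child-Pugh score and change from baseline in bilirubin, albumin and INR over the RILD window (1 week to 3 months after SBRT), flagging each item that was at 3 points at baseline.
2. The number of participants with fewer than 2 points of headroom (baseline 14 or 15), and the Child-Pugh-rise proportion repeated without them, labelled as a sensitivity result.
3. RILD events split by route: grade 4 AST/ALT, or Child-Pugh rise. This also makes clear which of the two RILD definitions in the protocol each event meets.

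Align footnote G of 6.8, whose liver panel omits albumin, with 6.2.2, which lists it; the Child-Pugh score needs it in any case. INR is already collected under 6.2.3.

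Splitting the rates into baseline strata is not worthwhile at this size: 0 events in 5 still has an exact upper limit of 52%.

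The cost is a few sentences and one or two small descriptive tables from data that 6.2.2 and 6.2.3 already call for. They will be imprecise at n = 15, and the liver safety picture may look less favourable. Ascites and encephalopathy have no continuous measure, so worsening beyond their top category will still depend on the CTCAE record.

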#### 9.2.4 ANALYSIS OF THE EXPLORATORY ENDPOINT

The QoL scores will be recorded over time (See Sections 6.1.8 and 6.8) using the EORTC QLQ-C30 and FACT-Hep questionnaires. Summary of QoLs and its change over time will be presented graphically using box plot and spaghetti plot, in addition to a summary table of QoL over time. No hypothesis testing is planned for QoL.

Descriptive statistical analysis, utilizing the efficacy analysis set, will be used to measure the proportion of histopathologic changes in irradiated tumor sites relative to uninvolved liver tissue will be measured.

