## 2.3 EXPLORATORY OBJECTIVES

Assess quality of life in HCC patients with advanced cirrhosis following liver SBRT. Examine SBRT-related histopathologic changes in explanted livers of patients with advanced cirrhosis.

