### 3. STUDY DESIGN AND ENDPOINTS

#### 3.1 DESCRIPTION OF THE STUDY DESIGN

*Refer to Section 9, Statistical Considerations, for additional information regarding statistical methods used in this study.*

This is pilot study to assess the feasibility of bridge-to-transplantation SBRT for patients with severe liver disease. Participants must meet the inclusion criteria, have none of the exclusion criteria, and have provided written informed consent before the conduct of any screening tests not performed routinely in their treatment.

In general, patients with CP-B8 or higher cirrhosis and non-metastatic HCC who have been listed or recommended to be listed for liver transplantation will be eligible for participation in this study. Eligible participants will undergo SBRT consisting of 40 Gy to be given in 5 fractions every other day provided that criteria for normal organ constraints are met (i.e.,  $\geq 700$  cc of uninvolved liver). In cases where normal organ constraints are not met, the dose will be iteratively de-escalated to two dose levels (35 Gy in 5 fractions, then 30 Gy in 5 fractions). If normal organ constraints are unable to be met at 30 Gy in 5 fractions, the participant will be considered ineligible for SBRT and considered a screen failure.

Following SBRT, the rate of radiation-induced liver disease (non-classical RILD) and associated toxicities will be evaluated, along with treatment response and an assessment of quality of life associated with SBRT. The proportion of participants that are successfully bridged to liver transplantation, and times to liver transplantation following SBRT will be recorded for each participant. Additional exploratory studies will assess SBRT-related histopathologic changes in explanted livers of participants with advanced cirrhosis. In these studies, pathologic treatment response in explanted livers will be evaluated, and regions of uninvolved liver both near and remote to the irradiated volume will be assessed for histopathologic changes consistent with RILD (e.g., obliteration of central veins, increased perisinusoidal reticulin network and hepatocyte necrosis).

This study aims to enroll 15 participants at OHSU. Participant data for primary, secondary, and exploratory endpoints will be collected by the site providing clinical care. The analyses of the data collected will take place at OHSU.

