### 3.2.3 EXPLORATORY ENDPOINT

Endpoint	Start	End
QoL scores for QLQ-C30 questionnaire		Death or 2-years after last SBRT dose, whichever occurs first
QoL scores for Functional Assessment of Cancer Therapy-Hepatobiliary (FACT-Hep) questionnaire	Screening	
Proportion of histopathologic changes in irradiated tumor sites relative to uninvolved liver tissue	Transplantation	Transplantation

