### **9.3 SAMPLE SIZE, POWER, ACCRUAL RATE AND STUDY DURATION**

#### **9.3.1 SAMPLE SIZE AND POWER**

The primary goal of this pilot study is to help identify unforeseen problems with a subsequent larger-scale clinical trial. We predict that there is a 20% probability that a particular patient's treatment plan will fail to meet all dosimetric constraints, most notably the 700 cc critical volume constraint for the liver minus GTV since many cirrhotic patients have small total liver volumes, rendering them ineligible for SBRT. A sample size of 15 patients will ensure that we will encounter at least one incidence of SBRT ineligibility at a 95% CI.

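### The explant endpoint contrasts irradiated tumour with uninvolved liver and does not carry forward the near-versus-remote liver reading planned in Section 3.1

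*Combined protocol and SAP*

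**What the plan says.** The exploratory objective in Section 2.3 is to "Examine SBRT-related histopathologic changes in explanted livers of patients with advanced cirrhosis".

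Section 3.1 describes how this will be done, and names two readings. First, "pathologic treatment response in explanted livers will be evaluated". Second, "regions of uninvolved liver both near and remote to the irradiated volume will be assessed for histopathologic changes consistent with RILD", with these examples of the changes sought: "obliteration of central veins, increased perisinusoidal reticulin network and hepatocyte necrosis".

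The endpoint and analysis text names a single contrast:

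- Synopsis, exploratory endpoint 3: at transplantation, "histopathologic changes in irradiated tumor sites relative to uninvolved liver tissue will be assessed".
- Section 3.2.3: "Proportion of histopathologic changes in irradiated tumor sites relative to uninvolved liver tissue".
- Section 9.2.4: a descriptive analysis in the efficacy analysis set will "measure the proportion of histopathologic changes in irradiated tumor sites relative to uninvolved liver tissue".

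Section 9 opens by referring the reader back to Section 3.1 for the detail of design and endpoints. No part of the document gives a grading scale, a sampling rule, a denominator for the proportion, or a definition of near and remote.

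**The concern.** The objective asks which changes in the liver are related to SBRT. A comparison of irradiated tumour with uninvolved liver changes two things together: the tissue (carcinoma or cirrhotic parenchyma) and the radiation received. These tissues would be expected to look different under the microscope without any radiation. The RILD features listed in Section 3.1 concern central veins, the perisinusoidal network and hepatocytes, so they describe liver parenchyma; scoring them in tumour does not measure liver injury.

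Section 3.1 already contains a better comparison. Near and remote uninvolved liver from the same explant share the same patient, the same cirrhosis and the same tissue type, and differ mainly in dose. That comparison appears in no endpoint and no analysis. This matters because Section 1.4.1 concedes, for clinical toxicity, that treatment effect is hard to tell from the natural decline of a cirrhotic liver. The trial has one arm, and the explant is its only tissue endpoint. Section 1.3 says the pilot should inform a larger trial, and an endpoint that is hard to interpret helps little with that.

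**Working it through.** No number in the plan depends on this endpoint. The only sample-size figure, 15 in Section 9.3.1, concerns SBRT ineligibility at an assumed 20%. It reproduces: ln(0.05)/ln(0.80) = 13.4, so 14 is the minimum, and 1 − 0.80^15 = 0.965. It does not bear on the explants except as the planned number of participants. The check is therefore a comparison of texts.

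**Step 1. What each contrast varies.**

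| Contrast | Where stated | Tissue type | Radiation |
|---|---|---|---|
| Irradiated tumour vs uninvolved liver | Synopsis, 3.2.3, 9.2.4 | differs | differs |
| Near vs remote uninvolved liver, same explant | 3.1 only | same | differs in degree |

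In the first row a difference could come from either factor, and nothing in the analysis separates them. In the second row tissue type is held constant.

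**Step 2. Is uninvolved liver the same as unirradiated liver?** No. Section 5.1.2 builds the PTV by adding a 5 mm margin around the gross tumour (or internal target) volume, and Section 5.1.3 prescribes dose to the PTV. Where that margin lies in liver, it is outside the contoured tumour yet treated. The comparator in Section 9.2.4 can therefore include both treated and lightly treated liver. The text does not say that the regions will be pooled, and does not say that they will be kept apart.

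**Step 3. Is remote liver free of dose?** Not necessarily. Table 3 sets a 15 Gy limit on a 700 cc critical liver volume, not zero dose. Section 1.2.1 also describes a study in which toxicity in Child-Pugh B patients was associated with larger liver volumes receiving low doses. Near versus remote is thus a contrast of higher with lower dose. It reduces confounding but does not remove it.

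**Step 4. Does any other section use the near and remote reading?** The synopsis, Section 3.2.3 and Section 9.2.4 do not. The clinical RILD endpoint in Section 3.2.2 rests on transaminases and Child-Pugh score, not on tissue.

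**Step 5. How much could the paired reading show?** Only transplanted participants supply explants, and the plan projects no number. If a feature were seen in none of n near-field regions, the upper exact two-sided 95% limit would be 1 − 0.025^(1/n):

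- n = 4: 60%
- n = 8: 37%
- n = 15 (every planned participant): 22%

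The values of n are assumptions covering a range. Reporting should stay descriptive and list each pair.

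**The case against.** The strongest reply is that Section 9 itself sends the reader to Section 3.1, so Section 9.2.4 may be a loose one-line summary of a design set out properly elsewhere. The near and remote tissue will be read in any case. The analysis is descriptive, no hypothesis test is planned, and a description of treated tumour beside background liver can still be reported.

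Much of this stands, and it limits the point. A reader might infer that the trial cannot show SBRT-related liver injury, that the objective in Section 2.3 is not met, or that the explants yield nothing usable. The documents do not support those readings: the objective is only to examine changes, Section 3.1 commits to the examination, and tumour response is interpretable on its own. A reader might also infer that Section 9.2.4 pools near and remote liver; it is silent on sub-regions, so pooling is possible but not stated.

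What does not stand is that the cross-reference settles the matter. It confirms that the reading is planned, but it does not change the contrast given in three concordant places. Being descriptive does not make that contrast attributable to radiation.

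It is also tempting to project the number of explants from the institutional cohort in Section 1.2.1: 13/51 = 25.5%, and 0.255 × 15 = 3.8. That cohort was retrospective, mixed SBRT with accelerated hypofractionation, and is not described as restricted to transplant candidates, whereas this trial requires listing or a recommendation to list (Section 4.1). The fraction may not transfer, and the flaw does not depend on it.

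**Conclusion.** The point holds as a mismatch between the design description and the endpoint and analysis text. As specified, the contrast cannot by itself attribute liver changes to SBRT, and the comparison better suited to that question has no endpoint or analysis. Its reach is one of the three exploratory endpoints in the synopsis, in transplanted participants only; primary, secondary and safety conclusions are unchanged.

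This rests on two assumptions: that the term for irradiated tumour sites means tumour and not the surrounding liver, as the separate terms in Section 3.1 suggest; and that near and remote regions can be told apart in the explant using the treatment plan. If the first is wrong, the endpoint text should say what the term covers.

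**What to change.** Align synopsis exploratory endpoint 3, Section 3.2.3 and Section 9.2.4 with Section 3.1 by stating two descriptive outputs:

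- (a) pathologic treatment response in irradiated tumours, reported on its own;
- (b) each RILD feature listed in Section 3.1, scored in near and in remote uninvolved liver and shown as within-participant pairs, with the number of explants stated.

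Define near and remote from the existing treatment plan, for example by distance from the PTV or by isodose, and state how each feature is scored. The tumour-versus-uninvolved-liver description need not be deleted, but it should not be used as evidence of SBRT-related liver injury. Add a sentence noting that remote liver may have received some dose.

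The cost is small. Section 3.1 already commits to assessing both regions, so no new tissue or reader is needed. The added work is the rewording, a working definition of near and remote, and a simple scoring convention. The remaining limitation is that the pairs will be few.
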